#### **9.3.5. Vital Sign**

Change from baseline in all vital signs, height, weight and BMI at each visit will be described. Number, mean, standard deviation, median, minimum, maximum, 1st quantile and 3rd quantile will be calculated.

Change from baseline in weight will be analysed using ANCOVA. The model includes the factors of treatment group, pooled site, interaction of pooled site with treatment group and baseline of corresponding parameters. If the interaction is not significant (2-sided alpha 0.1), then remove the interaction of pooled site with treatment group from model.

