3. The open-label treatment period (Visit 15) ends when subjects finish all the 52-week treatment. If early withdrawal occurs in the open-label treatment period, a termination visit needs to be completed within 7 days (the seventh day inclusive) after the last dose of study medications. In addition, a telephone follow-up for safety is conducted within 1 week after the last dose of study medications. If administration of the study medications has been stopped by the subjects for ≥ 7 days before early withdrawal, a termination visit needs to be completed as much as possible. The tests in the termination visit are the same as Visit 15.
4. All study medications are stopped in the safety observation period. Visit 16 is conducted by telephone at which adverse events and concomitant medications occurring in the safety observation period are recorded. The Investigator also follows up any adverse event occurring in the treatment period and without an outcome. Additional examinations are conducted if needed.
5. Physical examinations: general appearance, head, neck, chest (heart and lungs), abdomen, and limbs etc..
6. Vital signs: for Visit 1, blood pressure, pulse rate, breath rate, body temperature (axillary), height, weight. For other visits, all parameters except height are checked.
7. Routine blood test: hemoglobin, hematocrit, red blood cell count, white blood cell count, neutrophils, basophils, eosinophils, monocytes, lymphocytes, and platelet count.

8. Routine urine test: pH, specific gravity, protein, glucose, red blood cells, white blood cells, and ketone body.
9. Blood biochemistry: blood glucose; total bilirubin, alanine aminotransferase, aspartate aminotransferase, gamma-glutamyl transferase, alkaline phosphatase, albumin, total protein, lactate dehydrogenase, blood urea nitrogen, creatinine, uric acid, sodium, potassium, chloride, calcium, creatine kinase, creatine kinase isoenzyme, total cholesterol, high-density lipoprotein cholesterol, low-density lipoprotein cholesterol, triglyceride.
10. Virology test: hepatitis A virus antibody IgM (IgM anti-HAV), hepatitis B surface antigen (HBsAg), hepatitis B surface antibody (anti-HBs), hepatitis B core antibody IgM (IgM anti-HBc), hepatitis C virus antibody (anti-HCV), human immunodeficiency virus (HIV) antibodies.

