## 6. General Conventions For Data Handling

### 6.1. Premature Withdraw and Missing Data

In FAS, missing data will be imputed by LOCF method for ANCOVA. Missing values will be imputed with the last non-missing available on-treatment assessment (including unscheduled visit). If categorical parameter is derived with quantitative parameters, the derivation will be conducted after missing data imputation of quantitative parameter is completed.

When month and day of birth date are missing, then “July” and “15th” will be used to impute the missing month and missing day respectively. Same imputation rule will be used to impute the missing initial diagnosis date of type II diabetes.

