## 6.6. General rule of End-Of-Treatment Visit and Unscheduled Visit

For efficacy endpoint, if no scheduled visit value is missing, then corresponding unscheduled visit will not be included in analyses, otherwise the corresponding unscheduled visit will be used for missing data imputation (eg. LOCF). End-of-treatment visit of drop-out subjects will be mapped to nearest scheduled visit. Both of conventions below will be followed in determination.

1. The gap between end-of-treatment visit and nearest scheduled visit  $\leq 7$  days
2. Drug discontinuation before end-of-treatment visit  $\leq 7$  days.

For safety endpoint, if scheduled visit value is missing and followed by a consequent unscheduled visit, then the data at the nearest consequent unscheduled visit will be mapped on the corresponding missing scheduled visit (eg. LOCF). For the subjects who discontinued from the study early, end of trial (EOT) data will be mapped to the next scheduled visit.

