## 9. Secondary Statistical Analyses

### 9.1. Secondary Efficacy Analyses

Secondary efficacy analyses will be conducted in FAS and PPS.

The secondary efficacy endpoints include changes from baseline at each visit (except Week 24) of HbA1c, and changes from baseline at each visit of FPG, 0.5h PPG, 2h PPG, Fasting C-Peptide, 0.5-hour postprandial C-Peptide, 2-hour postprandial C-Peptide, Fasting Insulin, 0.5-hour postprandial Insulin, 2-hour postprandial Insulin. The same analysis method for the primary efficacy endpoint is used, i.e. MMRM.

HbA1c response rate and composite HbA1c response rate will be calculated on basis of data imputed using LOCF method. Odds ratio (OR) and its 95% CI between two treatment groups will be estimated using logistic regression method.

Other secondary endpoints, such as HOMA- $\beta$ , HOMA-IR, HOMA2- $\beta$ , HOMA2-IR, I0/G0,  $\Delta$  I30/  $\Delta$  G30,  $\Delta$  C30/  $\Delta$  G30,  $\Delta$  I120/  $\Delta$  G120 and change from baseline in DI will be analyzed and compared using covariance analysis model for each treatment group. Calculation will be based on data imputed by LOCF.

The value and change from baseline of HbA1c, fasting plasma glucose and 2-hour postprandial plasma glucose from the end of double-blind treatment period (Week 24) to the end of study (Week 52) will be summarized with descriptive statistics by group. One of the groups consists of subjects who were randomized into HMS5552 treatment group. Another group consists of subjects who were randomized into placebo group and then switch to HMMS5552 treatment in open-label treatment period. Data at the end of double-blind treatment period (Week 24) will be set as baseline to summarize the value and change from baseline at each visit in open-label treatment period.

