## **9.3. Safety Analyses**

Safety Analyses will be performed on Safety set.

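### The weight comparison in SAP 9.3.5 has no visit term, no stated analysis visit and no missing-data rule, and the beta-cell indices use LOCF ANCOVA, although the SAP's own MMRM would serve both

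*Supplement*

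**What the plan says.** **Weight.** SAP 9.3.5 first plans a by-visit summary: "Change from baseline in all vital signs, height, weight and BMI at each visit will be described". It then adds one between-group analysis: "Change from baseline in weight will be analysed using ANCOVA". On the model it says: "The model includes the factors of treatment group, pooled site, interaction of pooled site with treatment group and baseline of corresponding parameters". The interaction is dropped if it is not significant at a two-sided 0.1. No visit and no missing-data rule are given.

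**Measurement.** Weight belongs to the vital signs. After the Visit 1 list, the vital-signs footnote to the Schedule of Assessments adds: "For other visits, all parameters except height are checked". Vital signs are scheduled at Visits 1 and 4 to 15, which gives a baseline and six post-baseline double-blind values (Weeks 4, 8, 12, 16, 20 and 24).

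**Rules that might fill the gap.**
- SAP 6.1: "In FAS, missing data will be imputed by LOCF method for ANCOVA".
- SAP 9.3: "Safety Analyses will be performed on Safety set".
- SAP 6.6, for safety endpoints in subjects who stop early: "end of trial (EOT) data will be mapped to the next scheduled visit".

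**Beta-cell indices.** For HOMA-beta, HOMA-IR, HOMA2-beta, HOMA2-IR, I0/G0, the three delta ratios and the Disposition Index, SAP 9.1 specifies a covariance model and adds: "Calculation will be based on data imputed by LOCF". SAP 9.2 repeats the model.

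**The tool already in the plan.** SAP 8.1 analyses HbA1c by an MMRM without imputation. SAP 9.1.4, 9.1.5 and 9.2.1 to 9.2.6 use the same model for FPG, postprandial glucose, C-peptide and insulin.

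**The concern.** A model without a visit term takes one value per subject, so the analyst must decide which visit to use and what to do with subjects who have no value there. The SAP leaves both open for weight, and two programmers could produce different Week 24 results from it.

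The SAP meanwhile has an MMRM that would use all six visits without imputation. For the indices the inconsistency is explicit: glucose, insulin and C-peptide are modelled by MMRM, but quantities calculated from them are carried forward. No reason is given.

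Weight is the only vital sign given a between-group model, and absence of weight gain is part of the composite responder in SAP 9.2.7. Drop-out may be related to treatment: protocol 4.5.2 allows withdrawal for hyperglycemia, and protocol 9.1 allows for 20% drop-out. More such withdrawals on placebo are plausible, but the documents do not say so.

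**Working it through.** **1. The plan's own figure.** The only design figure concerns HbA1c (protocol 9.1: 300 and 150 subjects, difference 0.4, SD 1.2, two-sided 0.05, power 91.4%). SE = 1.2 × √(1/150 + 1/300) = 0.12, and 0.4/0.12 = 3.33. Power is 91.5% by the normal approximation and 91.4% by the noncentral t with 448 df, so the figure reproduces. It has no bearing on weight, for which the documents give no effect, SD, time course or drop-out pattern. Steps 3 to 6 are therefore illustrations.

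**2. What analysis does 9.3.5 describe?**

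| Reading | Basis | Consequence at Week 24 |
|---|---|---|
| LOCF | 6.1 ties ANCOVA to LOCF; the same model is used for the LOCF HbA1c sensitivity analysis (8.1.1) | A drop-out's last weight stands in for Week 24 |
| Observed values | 6.1 is worded for the FAS, while 9.3 puts weight on the Safety Set; 6.6 moves termination data only to the next scheduled visit | Most drop-outs are absent |
| One ANCOVA per visit | The preceding sentence describes weight by visit | As the second row |

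Under the second and third readings, a drop-out reaches Week 24 only if the next scheduled visit after termination is Week 24. With drop-out spread evenly over the five intervals, that is one drop-out in five.

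**3. LOCF, equal drop-out d.** Assume the last value falls evenly on Weeks 4, 8, 12, 16 and 20. The share of the true difference kept is 1 − d + d × (mean share of the final effect reached by then).
- Linear divergence: mean share = 12/24 = 0.5. At d = 0.20, 0.80 + 0.20 × 0.5 = **0.90**.
- Plateau by Week 12: mean share = (1/3 + 2/3 + 1 + 1 + 1)/5 = 0.8. At d = 0.20, 0.80 + 0.20 × 0.8 = **0.96**.

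**4. LOCF, unequal drop-out, linear change, true difference 1.0 kg.** Each arm's mean is multiplied by 1 − 0.5d, which is 0.95 at 10% drop-out and 0.85 at 30%.

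| Drug, placebo change (kg) | Drop-out drug / placebo | LOCF difference (kg) |
|---|---|---|
| −1, −2 | 10% / 30% | −0.95 + 1.70 = 0.75 |
| +1.5, +0.5 | 10% / 30% | 1.425 − 0.425 = 1.00 |
| −1, −2 | 30% / 10% | −0.85 + 1.90 = 1.05 |

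The bias can be towards zero, absent, or away from zero.

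**5. Completers only.** In large-sample simulations (200,000 per arm, linear trajectories), completers gave the true difference when drop-out was unrelated to weight. When drop-out depended on the previous weight change (12% to 29% per arm), the results in kg were:

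| Drug, placebo change | Simulated truth | Completers | MMRM-type estimate |
|---|---|---|---|
| +0.5, −0.5 | 1.01 | 0.92 | 1.02 |
| −0.5, −1.5 | 0.99 | 0.92 | 0.99 |
| +1.5, +0.5 | 1.02 | 0.90 | 1.02 |

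The MMRM-type estimate stayed near the truth in every scenario, all of which had drop-out that was random given the observed data.

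**6. Precision.** Against completers, the variance ratio is approximately [(1 − R²)/(1 − d) + R²] × (1 − d) = 1 − d × R². R² is the share of Week 24 variance explained by the last observed value, averaged over drop-out visits. Take correlation r between values four weeks apart, falling geometrically with the gap.
- r = 0.85: mean R² about 0.42; SE ratio √(1 − 0.2 × 0.42) = 0.96.
- r = 0.95: mean R² about 0.74; SE ratio √(1 − 0.2 × 0.74) = 0.92.

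The MMRM thus cuts the SE by about 4% to 8% at 20% drop-out.

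**7. Indices.** Insulin, C-peptide and the meal test are scheduled only at Weeks 12 and 24 after baseline in the double-blind period. The averages in step 3 do not apply to them, and no size is claimed.

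**The case against.** A reader might infer that the weight analysis is LOCF or completers only, that it shrinks the difference towards zero, and that drop-outs' data are thrown away. The documents do not support that.
- SAP 9.3.5 states neither method, and the LOCF rule is worded for a different analysis set.
- Shrinkage follows for LOCF when drop-out is similar and the arms keep diverging. It is not general (step 4). Common drift is plausible, because both arms receive diet and exercise guidance and Appendix 8 sets a weight-loss goal for overweight patients.
- Observed weights stay in the by-visit summaries, and protocol 4.6 seeks a termination visit within 7 days of the last dose.

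The strongest remaining case is that this is a one-line clarification on low stakes. Weight is not an efficacy endpoint, the protocol plans descriptive safety analysis, and no alpha or power depends on it. The SAP's change table labels the indices exploratory. Nor is MMRM the SAP's rule for every repeated measure. The remedy is also incomplete: hyperglycemia withdrawal is triggered by FPG, which a weight MMRM does not contain.

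All of this stands and limits the weight of the point. It does not show that a one-value or LOCF ANCOVA is as good as a model the SAP already specifies, and for the indices LOCF is explicit.

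**Conclusion.** The point holds as a minor one. For weight, the firm defects are the missing visit term, the unstated analysis visit and the unstated missing-data handling. Both Week 24 readings can bias the difference or lose precision, but neither the direction nor the size can be fixed from the documents. As illustrations, LOCF keeps 90% (linear) or 96% (plateau by Week 12) of the difference at 20% equal drop-out, and 75% to 105% at 10% versus 30%. Completers were about 7% to 12% below the simulated truth when drop-out followed earlier weight gain, and unbiased when it did not. All trajectories, correlations and drop-out patterns are assumptions. For the indices, LOCF ANCOVA is stated outright and is inconsistent with the MMRM used for their components. The primary conclusion is unaffected.

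**What to change.** In SAP 9.3.5, replace the ANCOVA paragraph with the SAP 8.1 MMRM on the Safety Set: change in weight at Weeks 4 to 24; treatment, visit, treatment-by-visit, pooled site and baseline weight; Week 24 difference with 95% CI.

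In SAP 9.1 and 9.2, use the same MMRM at Weeks 12 and 24 for all the beta-cell indices (HOMA-beta, HOMA-IR, HOMA2-beta, HOMA2-IR, I0/G0, the three delta ratios and the Disposition Index), each with its own baseline. Keep the LOCF ANCOVA as supportive at most.

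The cost is SAP wording and several re-programmed tables, the indices on both FAS and PPS. Existing MMRM code can be reused and no new data are needed. The site-by-treatment interaction check moves to the supportive ANCOVA. The SAP should also say that the MMRM assumes drop-out is explained by observed weights and the covariates, so withdrawal driven by FPG may not be fully addressed.

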### **9.3.6. 12-lead ECG**

Normality / abnormality of test results from baseline to post-treatment will be described. Subjects who are normal at baseline while abnormal with clinical significance after treatment or who are abnormal without clinical significance at baseline while abnormal with clinical significance after treatment will be listed.

### **9.3.7. Clinical Lab Test**

Lab test includes hematology parameters, chemistries parameters and routine urine parameters.

Number of subjects, mean, standard deviation, median, minimum, maximum, 1st quantile and 3rd quantile of continuous parameters will be calculated.

Number and percentage of categorical parameters will be summarized for each visit.

Normality / abnormality from baseline to post-treatment will be described on basis of results and determination from central lab.

Hematology parameters, chemistries parameters and routine urine parameters (quantitative parameters) will be classified by marks. If the tests have been done, results marked as “H/HT/HP/L/LT/LP” will be treated as abnormal while results without mark will be treated as normal. For routine urine parameters (quantitative parameters), “Negative/Normal” will be treated as normal while “positive/Trace/+~++++” will be treated as abnormal.

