## 7.5 Hy's Law

The Hy's Law is used in this study to monitor any possible drug-induced liver injury. The Hy's Law usually means that AST or ALT $> 3\times\text{ULN}$  and TBiL $> 2\times\text{ULN}$ , non-biliary increase (usually alkaline phosphatase  $< 2\times\text{ULN}$ ) without any other diseases for explanation of the increase. If ALT or AST is  $> 3\times\text{ULN}$ , and TBiL is  $> 2\times\text{ULN}$  without any other previous diseases for explanation of the increase, no matter whether alkaline phosphatase (ALP) increases or not, the Investigator must inform the subject of the central laboratory reports within 48 hours after awareness and ask the subject to return to the study site for central laboratory re-evaluation (if necessary, re-examinations at local laboratories can be taken). The Investigator conducts re-evaluation and closely monitors or follows-up with the subjects, or stops the study medications according to the Section 4.5.3 Subject withdrawal due to abnormal liver function and Appendix 6: Measures to be Taken for Abnormal Liver Functions in the protocol. The Investigator evaluates the etiology and conducts every essential examination to rule out drug-induced liver injury. If the Investigator confirms the event meets Hy's Law, the event needs to be reported as an SAE.

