### Screening and Run-in Periods

1. Subjects with active liver disease are screen failures.
2. Subjects with ALT or AST  $> 2.5 \times \text{ULN}$  or total TBiL  $> 1.5 \times \text{ULN}$  are screen failures.
3. If a subject has ALT or AST values higher than the upper limit of normal range but are  $\leq 2.5 \times \text{ULN}$ , or TBiL higher than the upper limit of normal range but are  $\leq 1.5 \times \text{ULN}$ , the Investigator is suggested to find out the cause for abnormal liver function parameters (the Checklist for Collecting Abnormal Liver Function Information in the Investigator's folder can be used). Subjects can continue the subsequent study only when the Investigator can ensure the abnormal liver function will not affect the safety assessment or subjects' completion of the entire study or study procedures.

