### Treatment Period

From Visit 4 to Visit 15 in this study

1. The Investigator can stop study medications based on subjects' actual condition if any of the following criteria is met (no need to wait for the retest results):
  - ALT or AST  $> 8 \times \text{ULN}$
  - ALT or AST  $> 5 \times \text{ULN}$  and lasts for  $\geq 14$  days
  - ALT or AST  $> 3 \times \text{ULN}$  and TBiL  $> 2 \times \text{ULN}$
  - ALT or AST  $> 3 \times \text{ULN}$  with liver damage symptoms (e.g., fatigue, nausea, vomiting, right upper abdominal pain or tenderness, fever, rash) or eosinophilia increase.

The Investigator should immediately provide active intervention or treatment to subjects and identify the cause. If necessary, consultation with hematologists is conducted. The Investigator should closely follow-up with the subjects until the liver function is recovered or returns to baseline status. The Investigator should record the relevant AEs or SAEs timely.

2. If subjects have ALT or AST  $> 3 \times \text{ULN}$  but do not meet withdrawal criteria, the Investigator must ask the subjects to come back to the research center and retake the liver function tests at the central laboratory within 48 hours after receiving the test report (local laboratory tests can

be done when necessary). The Investigator should record the relevant AE or SAE timely, and find out the cause for abnormal liver functions, and give necessary interventions. The Investigator should closely follow-up with the subjects until the liver function is recovered or returns to baseline status. The subjects can continue to receive treatment according to the visit schedule in the study protocol if the Investigator considers appropriate.

3. If subjects have ALT or AST higher than the upper limit of normal range but is $\leq 3\times$ ULN, the Investigator evaluates the clinical significance of the abnormal values (see Section 7.1.3 AEs Related to the Medical and Clinical Laboratory Examinations). If any AE criterion is met, an AE should be recorded. The Investigator needs to find out the cause for abnormal liver functions and give necessary interventions. The Investigator should closely follow-up with the subjects until the liver function is recovered or returns to baseline status. The subjects can continue to receive treatment according to the visit schedule in the study protocol if the Investigator considers appropriate.

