## 6.4. Multiple Measurement

For data of scheduled visit in summary analysis, if there are multiple values in a same scheduled visit, then the last one will be taken.

In listing, all values in scheduled and unscheduled visit will be displayed. If there are multiple values in one visit, then all will be displayed.

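### The SAP 9.3.7 shift display sorts liver tests into normal or abnormal, and no table counts subjects by multiple of ULN or pairs ALT/AST with TBiL

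*Supplement*

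**What the plan says.** **Analysis.** SAP 9.3.7 plans descriptive statistics for continuous laboratory parameters (n, mean, SD, median, minimum, maximum, quartiles) and a shift display: "Normality / abnormality from baseline to post-treatment will be described on basis of results and determination from central lab". A result carrying any of the marks H, HT, HP, L, LT or LP "will be treated as abnormal while results without mark will be treated as normal". Protocol v1.1 section 9.3.4 plans change from baseline at each visit and the same normal/abnormal comparison. Neither document mentions multiples of ULN in an analysis.

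**Entry.** Protocol 4.2 (criterion 18) and 4.3 (criterion 6) exclude ALT or AST above 2.5×ULN and TBiL above 1.5×ULN. Appendix 6 deals with the range below that. The item beginning "If a subject has ALT or AST values higher than the upper limit of normal range but are" within the 2.5×ULN ceiling (1.5×ULN for TBiL) lets the subject continue on the investigator's judgement.

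**On-treatment limits.** Protocol 4.5.3 and Appendix 6 allow study treatment to be discontinued in any of these cases:
- ALT or AST above 8×ULN
- ALT or AST above 5×ULN for at least 14 days
- ALT or AST above 3×ULN with TBiL above 2×ULN
- ALT or AST above 3×ULN with symptoms or eosinophilia

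Section 7.5 says that Hy's Law "is used in this study to monitor any possible drug-induced liver injury". For values above 3×ULN that do not meet the withdrawal criteria, Appendix 6 has the subject return and "retake the liver function tests at the central laboratory within 48 hours after receiving the test report".

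**Data handling.** SAP 6.4: for scheduled visits in summaries, "if there are multiple values in a same scheduled visit, then the last one will be taken". SAP 6.6, for safety: "if scheduled visit value is missing and followed by a consequent unscheduled visit", the nearest such unscheduled value is mapped to the missing visit.

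**The concern.** The protocol watches liver safety in multiples of ULN, but the SAP shows shifts in two classes. Those classes cannot separate a mild elevation from a large one. A subject who was mildly elevated at entry and becomes severely elevated therefore does not change class, while a subject who goes from normal to just above ULN does.

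The Week 24 analysis goes to the regulator for registration (SAP 3.1), and there is no independent monitoring committee (protocol 9.3.7, SAP 3.1). The planned tables are therefore the main comparison of laboratory safety between arms. A reader would expect to find in them how many subjects per arm crossed the limits the protocol itself set, and how many met the paired ALT/AST and TBiL condition. Neither count is planned.

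**Working it through.** The plan states no figure on this point, so the check is mostly a comparison of passages.

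**1. Shift display.** Take a subject at 2×ULN at baseline, which entry permits, who reaches 9×ULN on treatment. Both results carry a high mark, so the entry is abnormal to abnormal. A subject who goes from below ULN to 1.05×ULN is entered as normal to abnormal. The display counts the second and not the first.

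**2. Match with the protocol limits.** I looked for each limit in SAP 9.3.2 (adverse events), 9.3.7 (laboratory) and protocol 9.3.4.
- Subjects above 3×, 5× or 8×ULN by arm: none planned.
- TBiL above 2×ULN by arm: none planned.
- ALT/AST above 3×ULN together with TBiL above 2×ULN in the same subject: none planned.
- Worst on-treatment value per subject: none planned.

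By contrast, SAP 9.3.6 lists subjects whose ECG was abnormal without clinical significance at baseline and becomes clinically significant. The SAP thus recognises worsening within the abnormal class for ECG, but has no counterpart for liver tests.

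**3. Arm means.** Inputs: 300 subjects per HMS5552 arm from the 450 planned at 2:1, or 376 at the stated maximum. The number of subjects affected, k, is assumed. Each is taken from 2.5× to 8.01×ULN.

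Shift in arm mean = k × (8.01 − 2.5) / n = k × 5.51 / n

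- n = 300: k = 1 gives 0.018; k = 3 gives 0.055; k = 5 gives 0.092×ULN.
- n = 376: k = 1 gives 0.015; k = 3 gives 0.044; k = 5 gives 0.073×ULN.
- Crossing 3×ULN only just (to 3.01×ULN), k = 5, n = 300: 5 × 0.51 / 300 = 0.009×ULN.

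Means would hardly show such cases, and the shift table would show none of them as a change.

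**4. Handling rules.** Central-laboratory results reach sites within 72 hours (protocol 7.8), and the Appendix 6 retest follows within 48 hours of the report. A retest therefore normally falls on a later day.
- Scheduled value is the peak and the retest is recorded as unscheduled: the scheduled value is not missing, so it stays in the summary. The peak is kept.
- Unscheduled value is higher than an available scheduled value: the unscheduled value does not enter the summary. The peak is absent.
- Two values recorded under one scheduled visit, the first higher: 6.4 keeps the second. The peak is absent.
- Early discontinuation: end-of-trial safety data are mapped to the next scheduled visit (6.6), so termination-visit results are included.

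The documents do not say under which visit label a retest is recorded, so how often the third case arises is unknown.

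**The case against.** The strongest reply is that the information reaches the analysis by other routes.

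- **Maximum and change.** SAP 9.3.7 plans the maximum and quartiles, and protocol 9.3.4 plans change from baseline by visit. A scheduled value of 9×ULN could appear as the arm's maximum at that visit.
- **Adverse events.** Appendix 6 has a relevant AE or SAE recorded when ALT or AST exceeds 3×ULN. Protocol 7.1.3 makes a laboratory abnormality an AE when it suggests toxicity that is new or worse than baseline, which covers the subject who was already abnormal. Hy's Law cases confirmed by the investigator are SAEs (7.5). SAP 9.3.2 tabulates AEs, SAEs and AEs leading to withdrawal by arm.
- **Listings.** All scheduled and unscheduled values are listed (SAP 5 and 6.4).
- **Table shells.** SAP section 4 refers to attached shells that are not shown and may hold more.

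Most of this stands, and it limits the point. A reader might infer that the laboratory tables are blind to liver injury, or that AE reports alone would carry it. The maxima, change summaries and listings rule that out.

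The routes still do not supply the missing counts. A maximum is one number per arm and visit, and it cannot pair ALT with TBiL in one subject. Listings make no comparison between arms. AE severity is functional (protocol 7.2.4), so a symptom-free 9×ULN value could be graded mild and share a term with a small rise.

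**Conclusion.** The point holds as a gap in the planned safety display. The two-class shift conceals worsening in subjects who are above ULN at baseline, and no planned summary counts subjects by arm at the protocol's own ULN limits or in the paired ALT/AST and TBiL condition. A peak can also be absent from the summaries when it is seen at an unscheduled test, or when another value under the same visit follows it.

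Two wider readings are tempting but not supported.
- A reader might infer that the handling rules lose the peak in general. In the usual retest sequence the scheduled value that triggered the retest stays in.
- A reader might extend the point to other laboratory tests such as triglycerides. The 5.7 mmol/L figure is an entry criterion, and the protocol sets no on-treatment triglyceride limit.

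The limits in 4.5.3 also permit discontinuation depending on the subject's condition; they do not compel it.

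The size in this trial cannot be given, because the documents do not state how many subjects are above ULN at baseline; the arithmetic on means rests on assumed counts. The primary efficacy conclusion is not affected. The change is worth making because the present rule hides a pattern the protocol says it monitors, and the remedy is cheap.

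**What to change.** In SAP 9.3.7 add tables by arm and by period (double-blind, open-label). They should give the number and percentage of subjects whose worst post-baseline value, over all scheduled, unscheduled and end-of-treatment results, exceeds the limits already in protocol 4.5.3 and 7.5:

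- ALT or AST above 3×, above 5× and above 8×ULN
- TBiL above 2×ULN
- ALT or AST above 3×ULN together with TBiL above 2×ULN

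Cross-tabulate each by baseline category (at or below ULN; above ULN). Leave the upper baseline category open-ended: eligibility is judged on Visit 3 results while the baseline sample is taken at Visit 4, so a baseline value may lie above the entry ceiling.

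State that 6.4 (last value) and 6.6 (scheduled before unscheduled) do not apply to these worst-value tables. State also which baseline serves the open-label period, since SAP 6.3 fixes a safety baseline for the double-blind period alone.

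The cost is SAP wording and a few extra tables from central-laboratory data already collected. No test, visit or clinical rule changes.
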